Examples of such events are intensive treatment in an emergency room or at home for allergic bronchospasm, blood dyscrasias or convulsions that do not result in hospitalisation or development of dependency or abuse. Any suspected transmission via a medicinal product of an infectious agent is also considered a serious adverse reaction.

The following events will be handled as “deemed serious for any other reason”. An AE which possibly leads to disability will be reported as an SAE.

AEs considered “Always Serious”

In accordance with the European Medicines Agency initiative on Important Medical Events, Boehringer Ingelheim has set up a list of further AEs, which by their nature, can always be considered to be “serious” even though they may not have met the criteria of an SAE as given above.

The latest list of “Always Serious AEs” can be found in the RDC system, a remote data capture system which allows the entry of trial data at the trial site. These events should always be reported as SAEs as described in [section 5.2.2.2](#).

Cancers of new histology and exacerbations of existing cancer must be reported as a serious event regardless of the duration between discontinuation of the drug and the occurrence of the cancer.

Adverse events of special interest (AESIs)

The term AESI relates to any specific AE that has been identified at the project level as being of particular concern for prospective safety monitoring and safety assessment within this trial, e.g. the potential for AEs based on knowledge from other compounds in the same class. AESI need to be reported to the Sponsor's Pharmacovigilance Department within the same timeframe that applies to SAE, see [Section 5.2.2.2](#).

The following are considered as AESIs:

Hepatic injury

A hepatic injury is defined by the following alterations of hepatic laboratory parameters:

- an elevation of AST and/or ALT ≥ 3 fold ULN combined with an elevation of total bilirubin ≥ 2 fold ULN measured in the same blood draw sample, and/or
- marked peak aminotransferase (ALT, and/or AST) elevations ≥ 10 fold ULN

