AE reporting to sponsor and timelines

The Investigator must report SAEs, AESIs, and non-serious AEs which are relevant for the reported SAE or AESI, on the BI SAE form via fax immediately (within 24 hours of awareness) to the Sponsor's unique entry point (country specific contact details will be provided in the ISF). The same timeline applies if follow-up information becomes available. In specific occasions the Investigator could inform the Sponsor upfront via telephone. This does not replace the requirement to complete and fax the BI SAE form.

1. All SAEs and AESIs must be reported immediately to the head of the trial site.
2. With receipt of any further information to these events, a follow-up SAE form has to be provided. For follow-up information the same rules and timeline apply as for initial information.

Information required

Proprietary confidential information © 2017 Boehringer Ingelheim International GmbH or one or more of its affiliated companies

For each AE, the Investigator should provide the information requested on the appropriate (e)CRF pages and the BI SAE form (if applicable). The Investigator should determine the causal relationship to the trial medication.

The following should also be recorded as an (S)AE in the eCRF and on the SAE form (if applicable):

- Worsening of the underlying disease or of other pre-existing conditions
- Changes in vital signs, ECG, physical examination and laboratory test results, if they are judged clinically relevant by the Investigator.

If such abnormalities already pre-exist prior trial inclusion they will be considered as baseline conditions.

All (S)AEs, including those persisting after individual subject's EOT must be followed up until they have resolved, have been sufficiently characterized, or no further information can be obtained.

Pregnancy

Once the male subject has been enrolled in the clinical trial and has taken trial medication, and if a partner of the male trial participant becomes pregnant, the investigator must report any drug exposure during pregnancy in a partner of the male trial participant immediately (within 24 hours) by means of Part A of the Pregnancy Monitoring Form to the sponsor's unique entry point, after a written consent of the pregnant partner.

The outcome of the pregnancy associated with the drug exposure during pregnancy must be followed up and reported to the sponsor's unique entry point on the Pregnancy Monitoring Form for Clinical Trials (Part B).

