### **7.8.1 Adverse events**

AEs will be coded with the most recent version of MedDRA.

The analyses of AEs will be descriptive in nature. All analyses of AEs will be based on the number of subjects with AEs and not on the number of AEs.

For analysis, multiple AE occurrence data on the eCRF will be collapsed into one event provided that all of the following applies:

- All AE attributes are identical (lower level term, intensity [CTCAE grade Version 4.03], action taken, therapy required, seriousness, reason for seriousness, relationship, outcome, AESI)
- The occurrences were time-overlapping or time-adjacent (time-adjacency of two occurrences is given if the second occurrence started at most 1 hour after the first occurrence ended)

For further details on summarization of AE data, please refer to 'Handling and summarization of adverse event data for clinical trial reports and integrated summaries' ([6](#)) [001-MCG-156] and "Handling of missing and incomplete AE dates" ([3](#)) [001-MCG-156\_RD-01].

The analysis of AEs will be based on the concept of treatment emergent AEs. That means that all AEs will be assigned to the screening phase or on-treatment phase as defined in [Section 6.1](#).

An overall summary of AEs will be presented. This overall summary will comprise summary statistics for the class of other significant AEs according to ICH E3 and for the class of AESIs.

**CTP:** *The following are considered as AESIs in this trial:*

*Hepatic injury*

*A hepatic injury is defined by the following alterations of hepatic laboratory parameters:*

- *an elevation of AST and/or ALT > 3 fold upper limit normal (ULN) combined with an elevation of total bilirubin > 2 fold ULN measured in the same blood draw sample, and/or*
- *marked peak aminotransferase (ALT and/or AST) elevations  $\geq 10$  fold ULN*

The investigator had to classify on the eCRF whether an observed AE was an AESI or not.

According to ICH E3 (8), AEs classified as ‘other significant’ need to be reported and will include those non-serious and non-significant AEs

- (i) which are marked haematological or other lab abnormalities, or
- (ii) which were reported with ‘action taken = discontinuation’ or ‘action taken = reduced’, or
- (iii) which lead to significant concomitant therapy as identified by the Clinical Monitor/Investigator at a Medical Quality Review Meeting.

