The frequency of subjects with AEs will be summarised by treatment, primary SOC and preferred term. AEs which were considered by the investigator to be drug related (primary endpoint) will be summarised separately. Separate tables will also be provided for subjects with SAEs, subjects with AESIs and subjects with other significant AEs (according to ICH E3 (8)). The frequency of subjects with AEs and the frequency of subjects with AEs considered by the investigator to be drug related will also be summarised by maximum grade of CTCAE (version 4.03), primary SOC and preferred term.

The SOCs will be sorted according to the standard sort order specified by the EMA, preferred terms will be sorted by total frequency (within SOC).

For disclosure of AE data on ClinicalTrials.gov, the frequency of subjects with non-serious AEs occurring with an incidence of greater than 5 % (in preferred terms) will be summarised by treatment, primary SOC and preferred term. The frequency of subjects with SAEs will also be summarised.

For disclosure of AE data in the EudraCT register, the frequency of AEs, the frequency of non-serious AEs with an incidence of greater than 5 % (in preferred terms) and the frequency of SAEs will be summarised.

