## **7.8.2     Laboratory data**

The analyses of laboratory data will be descriptive in nature and will be based on BI standards ([7](#)). Laboratory analyses will be based on normalised values, i.e., for a given laboratory parameter, values will be transformed to a standard unit and a standard reference range before statistical analysis.

**CTP:** *Laboratory data will be compared to their reference ranges. Values outside the reference range will be flagged. Additionally, differences from baseline will be evaluated.*

Descriptive statistics of laboratory values over time and for the difference from baseline (see [Section 6.7](#)) will be provided. Frequency tables of changes between baseline and last value on treatment with respect to the reference range will be presented.

Possibly clinically significant abnormal laboratory values are only those identified either in the Investigator's comments or at the RPM/DBLM at the latest. It is the Investigator's responsibility to decide whether a lab value is clinically significant abnormal or not. Standard or project-specific rules for flagging clinically significant values in an automated manner will not be applied in this study.

Clinically relevant findings in laboratory data will be reported as baseline conditions (at screening) or as AEs (during the trial) if judged clinically relevant by the investigator, and will be analysed as such.

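### The hepatic-injury AESI is defined by numeric laboratory limits, but the SAP counts it only from the investigator's eCRF classification, with no stated check against the laboratory data

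*SAP*

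**What the plan says.** **Definition.** Protocol 5.2.2.1 names one AESI: "A hepatic injury is defined by the following alterations of hepatic laboratory parameters". The first criterion is "an elevation of AST and/or ALT ≥ 3 fold ULN combined with an elevation of total bilirubin ≥ 2 fold ULN", with both measured in the same blood draw. The second is "marked peak aminotransferase (ALT, and/or AST) elevations ≥ 10 fold ULN". Either is sufficient, and no clinical judgement enters the definition.

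**How a laboratory change becomes an adverse event.** Protocol 5.2.2.2 lists what must also be recorded as an adverse event, including "Changes in vital signs, ECG, physical examination and laboratory test results, if they are judged clinically relevant by the Investigator". SAP 7.8.2 repeats that condition.

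**How the AESI is counted.** SAP 7.8.1 states: "The investigator had to classify on the eCRF whether an observed AE was an AESI or not". It then plans the output: "Separate tables will also be provided for subjects with SAEs, subjects with AESIs and subjects with other significant AEs".

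**What happens to the laboratory data.** SAP 7.8.2 keeps flags for values outside the reference range, descriptive statistics over time, and shift tables from baseline to the last on-treatment value. Possibly clinically significant values come only from investigator comments or from the report planning/database lock meeting. It then says: "Standard or project-specific rules for flagging clinically significant values in an automated manner will not be applied in this study". SAP section 7 states that individual values will be listed for all subjects.

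**The SAP's restatement of the definition.** SAP 7.8.1, in text labelled as coming from the protocol, gives the combined criterion as "an elevation of AST and/or ALT > 3 fold upper limit normal (ULN) combined with an elevation of total bilirubin > 2 fold ULN".

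**The concern.** The event is objective and should be computable from AST, ALT and total bilirubin, all of which are routine laboratory tests under protocol 5.2.3. The planned count nevertheless depends on two human steps: the finding must be recorded as an adverse event, and that event must be classified as an AESI. If either step fails, the AESI table can show no cases while the laboratory data hold a subject who meets the protocol definition. If no adverse event is recorded at all, the case also cannot enter the primary endpoint, which counts subjects with drug-related adverse events. The groups are small, so a single case changes what the table appears to say.

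**Working it through.** The documents give no figure for this point, so the check compares the texts and adds simple arithmetic.

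**1. Could another planned output reveal a missed case?**

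| Planned output (SAP) | Applies 2x, 3x or 10x ULN? | Pairs same-draw bilirubin? |
|---|---|---|
| AESI table (7.8.1) | Only through the investigator's classification | Only through the investigator's classification |
| Other significant adverse events, including marked laboratory abnormalities (7.8.1) | No; starts from recorded adverse events | No |
| Reference-range flags (7.8.2) | No; they mark any value outside the range | No |
| Statistics over time (7.8.2) | No | No |
| Shift table, baseline to last value (7.8.2) | No; relative to the reference range | No |
| Individual listings (section 7) | No; values shown, definition not applied | No |

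The shift table has a further limit. SAP 6.1 runs the on-treatment phase to trial termination. The protocol flow chart places the end-of-trial safety laboratory on Days 42 to 48, and the last dose is on Day 28. The last value can therefore fall 42 − 28 = 14 to 48 − 28 = 20 days after dosing. A peak that has resolved by then can appear as normal to normal.

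**2. Weight of one case.** Protocol 7.6 gives 9 active and 3 placebo subjects per dose group and ethnicity, in four groups: 4 × 12 = 48, which agrees with the stated total. Active subjects number 3 × 9 = 27 Japanese and 4 × 9 = 36 overall. The contribution of one case is 1/n, with exact (Clopper-Pearson) two-sided 95% limits:

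| Active subjects | One case counted | Case missed |
|---|---|---|
| 9 (one group) | 1/9 = 11.1% (0.3% to 48.2%) | 0/9, upper limit 33.6% |
| 27 (all Japanese) | 1/27 = 3.7% (0.1% to 19.0%) | 0/27, upper limit 12.8% |
| 36 (all active) | 1/36 = 2.8% (0.1% to 14.5%) | 0/36, upper limit 9.7% |

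The documents give no basis for a probability that a case is missed, so none is calculated.

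**3. Protocol limits against SAP limits.** Both definitions were applied to test pairs of aminotransferase and bilirubin, in multiples of ULN:

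| AST or ALT | Bilirubin | Protocol 5.2.2.1 | SAP 7.8.1 |
|---|---|---|---|
| 3.0 | 2.0 | met | not met |
| 3.0 | 2.5 | met | not met |
| 4.0 | 2.0 | met | not met |
| 3.1 | 2.1 | met | met |
| 10 | 1 | met | met |

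The two texts disagree only when a value lies exactly on a limit of the combined criterion. The second criterion uses the same inclusive limit in both.

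**The case against.** The strongest reply is that protocol 5.2.2.1 does not leave hepatic injury to the general rule on clinical relevance. Qualifying laboratory results themselves constitute a hepatic injury alert, and follow-up with the DILI checklist is required. Protocol 5.2.2.2 requires all AESIs to be documented on the eCRF and reported within 24 hours. A case left out would be a departure from the protocol, and might still leave a trace in the checklist or on the SAE form. The report planning/database lock meeting is a later manual review, and sponsor functions see accumulating data unblinded. All of this stands. It makes an omission less likely, but it does not supply a check of the AESI table against the laboratory data.

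Several stronger readings are tempting, and the documents do not support them:

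- *All automated laboratory flagging is switched off.* It is not. SAP 7.8.2 excludes only automated flagging of clinically significant values; reference-range flags stay. That sentence also concerns a different category from AESIs, so deleting it alone would not create a derivation.
- *A missed case would vanish from the report.* It would be absent from the AESI table, but values in the database would still be listed.
- *Hepatic injury is an established signal for this drug.* No visible passage reports one. The AESI label marks a concern for monitoring.
- *No reconciliation exists anywhere.* This cannot be verified. Protocol 8.2 refers data-quality procedures to the data management and analysis plan. SAP 6.1 refers implementation to the analysis dataset plan, and SAP 7.8.1 and 7.8.2 cite internal standards. None of these was available.

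The percentages also deserve caution: 1/9 is the weight of any single misclassified event in a group of nine, and the analysis is descriptive.

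**Conclusion.** The point holds as a gap in the visible plan. The only AESI has a purely numeric definition, its table rests on the investigator's classification of a recorded event, and no visible text checks that classification against AST, ALT and bilirubin. A case would be missed only through an omission or a judgement that it was not clinically relevant. The documents show that this can happen, not that it is likely. If it did, one case would be 11.1 percentage points in an active group of 9. The conclusion assumes that the unseen plans and standards contain no such reconciliation. If they do, the SAP needs only to say so.

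The mismatch between the SAP's strict inequalities and the protocol's inclusive ones is a plain inconsistency and does not depend on that assumption.

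**What to change.** In SAP 7.8.2, add an exception to the exclusion of automated rules:

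- On the Treated Set, apply the hepatic-injury criteria of protocol 5.2.2.1 to every post-dose sample held in the database. Use the original rather than the normalised values, the local ULN, and bilirubin from the same draw for the combined criterion.
- List and count the subjects who meet the criteria, by treatment, beside the investigator-classified AESIs.
- Query every mismatch before database lock.
- Reconcile the combined criterion in SAP 7.8.1 with protocol 5.2.2.1, since the SAP presents its version as protocol text.

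The cost is one derived flag, one table or listing, and one check before lock. No additional sampling is needed. The documents do not say that every unscheduled result reaches the database, which is why the rule is limited to samples held there. The downside is that the derived count may exceed the investigator-classified count, and the clinical trial report would then have to explain the difference.

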## **7.8.3     Vital signs**

The analyses of vital signs will be descriptive in nature. Descriptive statistics of vital signs over time and for the difference from baseline (see [Section 6.7](#)) will be provided.

Clinically relevant findings in vital signs data will be reported as baseline conditions (at screening) or as AEs (during the trial) if judged clinically relevant by the investigator, and will be analysed as such.

### **7.8.5 Others**

Physical examination findings and ophthalmological examination findings (exclusion of cataract) will be reported as relevant medical history/baseline condition (i.e., a condition already existent before intake of study drug) or as AE and will be summarised as such. No

separate listing or analysis of physical examination or ophthalmological examination findings will be prepared.

## **10. HISTORY TABLE**

Table 10: 1 History table

| Version | Date
(DD-MMM-YY) | Author | Sections
changed | Brief description of change                                    |
|----------------|-----------------------------|---------------|-----------------------------|---|
| Initial        | 31-MAY-17            |               | None                        | This is the initial TSAP with necessary information for trial conduct |
| Final          | 29-JAN-18            |               | None                        | This is the final TSAP without any modificalon                        |
